## SPECIFIC RISKS AND PROTECTION MEASURES

### 1. Fluoroscopic Procedures

As with every clinical study, there may be some risks. However, doses of radiation exposure received will be much lower than those known to produce detectable health effects. Previously reported literature shows that fluoroscopy-based procedure (angiography) on the lower limb result in a typical effective dose of 0.83 mSv per min (0.083 rem per min) (Verdun). Mettler, et al have reported that the typical effective dose for a conventional knee procedure is 0.005 mSv (0.0005 rem). According to either estimate, the additional risk of a fluoroscopic procedure involving the knee ranges between "Negligible" to "Low" for a 2 minute exam (Verdun). A previous fluoroscopy TKA study conducted at another hospital with a 2 minute on-time limit shows that the average effective dose was 0.14 mSv (0.0014 rem) with a maximum dose of 0.27 mSv (0.027 rem). The additional risk for all subjects in this previous study would be considered "Negligible". To account for patient variability and differences in imagining techniques, all subjects enrolled in this study will receive less than 2 rem. 2 rem is considered "Low" risk. It is unlikely that anyone in this study will approach the 2 rem limit. Since the fluoroscopy data will be collected in one session, there will only be one day in which the participants will be exposed to this amount of radiation.

In conclusion, a participant who will be fluoroscoped for less than two minutes will be exposed to a *maximum* amount of only 2.0 rems of radiation. This means that the maximum total exposure rate will be less than 2 rems per subject for the entire experiment. The participant's knee joint will be fluoroscoped using negligible to low risk levels of radiation according to published literature.

The participant has the right to stop the procedure at any time; researchers or the RT can end the procedures at any time if they feel the participant is at risk, but the participant can choose to remain in the study if s/he feels that there is no risk to her/his surgical procedure or recuperation.

We are estimating a total maximum time of 45 minutes to permit the subject time to complete the IC form, ask any questions s/he may have, practice the activities or repeat any activities that could not be completed, and collect all necessary fluoroscopy data from each subject.

---

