### **Data Collection**

University of Tennessee researchers with experience conducting fluoroscopic research studies, as well as either a PI or Co-PI for the study, and possibly [name] staff will be present during the fluoroscopy procedure to walk subjects through the activities. A radiation technician (RT) employed by Parkwest Medical Center will collect fluoroscopic video while subjects perform the following activities: deep knee bend. For the DKB activity, the subjects were instructed to begin at full extension on a raised platform and take a step back while flexing their knee as far as they could, in order to obtain a maximum flexion value for each subject. For this activity, images were taken at 30° increments from full extension (0°) to maximum flexion (MAX) for the entire flexion/extension cycle. Patients were examined while performing these activities using a C-Arm type fluoroscopic unit. The fluoroscopic videos were captured digitally and transferred to a secure lab network for subsequent analysis.

If a subject does not meet the inclusion criteria, s/he will not be tested. If the participant still meets all study criteria, s/he will be asked to practice the activities to ensure s/he can comfortably complete them and experience no pain with the hospital fluoroscopy machine off (no radiation). The practice portion of the data collection without radiation will not be video-recorded. During the fluoroscopy procedure, the RT will follow the motion of the implanted knee with the fluoroscopy machine; only the knee joint (from the fluoroscopy machine) will be recorded on the fluoroscopy footage. The participant will be allowed to rest as necessary and be instructed to stop the activity at the first sign of pain.

Multiple trials of each activity may be conducted to ensure usable images have been acquired to complete the study. Radiation time will be kept as low as reasonably achievable (ALARA) and will not exceed two minutes. The RT will start the fluoroscope just prior to the subject beginning each activity trial and will stop the fluoroscope immediately after the subject completes each activity trial to ensure that the subject is not exposed during idol periods. Fluoroscopy on-time will be recorded on each subject's IC.

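### Do the tenfold mSv/rem mismatch and the wide 2-rem ceiling in the radiation section call for a change to the plan?

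*Combined protocol and SAP*

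**What the plan says.** The section headed 1. Fluoroscopic Procedures gives four doses, each in mSv and in rem:

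- a lower-limb angiography rate from the literature, with a "typical effective dose of 0.83 mSv per min (0.083 rem per min");
- a literature value under which "the typical effective dose for a conventional knee procedure is 0.005 mSv (0.0005 rem");
- the mean and the maximum from a previous knee-replacement fluoroscopy study with a two-minute on-time limit: "the average effective dose was 0.14 mSv (0.0014 rem) with a maximum dose of 0.27 mSv (0.027 rem").

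It classes the added risk for everyone in that previous study as Negligible.

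It then sets a ceiling for the present study: "all subjects enrolled in this study will receive less than 2 rem". The reason given is "To account for patient variability and differences in imagining techniques". The section rates 2 rem as Low risk and adds: "It is unlikely that anyone in this study will approach the 2 rem limit". Its concluding paragraph ties the ceiling to on-time, saying that "a participant who will be fluoroscoped for less than two minutes will be exposed to a" maximum of 2.0 rem.

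The Data Collection section holds the working controls. On-time is capped at two minutes, exposure is kept as low as reasonably achievable, and the fluoroscope runs only around each activity trial. On what is written down, it says "Fluoroscopy on-time will be recorded on each" subject's consent form. The available text does not mention recording a dose or a dose rate.

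**The concern.** Three things catch the eye.

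First, the previous study's mean does not convert by the factor used everywhere else in the paragraph. If the mSv figure is the right one, the rem figure understates the mean dose tenfold, in the unit in which the ceiling is set. That study is also the closest evidence offered, since it used the same type of examination with the same on-time limit.

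Second, 2 rem is presented as what two minutes of fluoroscopy can produce at most, yet nothing quoted in the section yields that number.

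Third, the promise is made in rem while the recorded quantity is time. Dose is rate multiplied by time, so time alone does not demonstrate compliance.

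The exposure is for research only. The Benefits section disclaims any intended direct benefit, and Clinical Observations says no radiology report is produced. The risk statement is what justifies the exposure. If its figures were wrong in a way that altered the risk class or loosened a limit, that would matter.

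**Working it through.** **Inputs.** The four mSv/rem pairs, the 2-rem ceiling and its stated reason come from 1. Fluoroscopic Procedures. The two-minute cap and the recording of on-time come from Data Collection.

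**Step 1: conversion factor in each pair (mSv divided by rem).**

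| Quantity | mSv | rem | mSv per rem |
|---|---|---|---|
| Angiography rate, per minute | 0.83 | 0.083 | 10 |
| Conventional knee procedure | 0.005 | 0.0005 | 10 |
| Previous study, mean | 0.14 | 0.0014 | 100 |
| Previous study, maximum | 0.27 | 0.027 | 10 |

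Three pairs reproduce and the mean does not. At 10 mSv per rem:

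- if 0.14 mSv is right, the rem value is 0.14 / 10 = 0.014;
- if 0.0014 rem is right, the mSv value is 0.0014 × 10 = 0.014.

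The ratio of maximum to mean is 0.27 / 0.14 = 1.9 in mSv and 0.027 / 0.0014 = 19 in rem as printed. The first is the more ordinary spread under a common time limit, so the rem figure is the likelier slip. That is an inference. The document does not settle it.

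**Step 2: does anything depend on the mean?** The Negligible label is applied to all subjects of the previous study, so the maximum governs it, and 0.27 mSv = 0.027 rem is consistent. Under either reading the mean lies below that maximum (0.014 or 0.0014 rem against 0.027 rem). The 2-rem ceiling and the two-minute cap are not computed from the mean, and the Data Analysis section does not use it.

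**Step 3: ceiling against the highest quoted rate.**

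- Dose in two minutes: 0.83 mSv/min × 2 min = 1.66 mSv = 0.166 rem.
- Ceiling: 2 rem = 20 mSv.
- Ceiling over two-minute dose: 20 / 1.66 = 12.05.
- Ceiling over previous maximum: 20 / 0.27 = 74.

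The section calls 0.83 mSv/min typical, not maximal. A typical dose of 0.166 rem under an upper bound of 2 rem is not a contradiction. The section gives a reason for the margin and says that the bound is unlikely to be approached.

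**Step 4: what on-time can and cannot show.**

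- Rate needed to reach the ceiling within the cap: 20 mSv / 2 min = 10 mSv/min, which is 10 / 0.83 = 12 times the highest quoted rate.
- Time needed at the quoted rate: 20 / 0.83 = 24.1 min, about 12 times the cap.

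On-time does not measure dose. With a cap of two minutes, however, a breach of the ceiling would need a rate 12 times the highest one the document cites.

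**The case for a change.** The strongest case for acting is that the unit mismatch is certain and sits in a safety statement. Its likelier direction understates exposure, and correcting it costs almost nothing. The stated reason for the wide ceiling is variation between patients and imaging technique, which is exactly what on-time cannot capture. A promised limit ought to be derivable and checkable, and here it is neither. The conclusion even calls a total in rem a rate.

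Parts of this stand. The two figures for the mean cannot both be right and should be checked against the previous study's data. No derivation of 2 rem is shown. On-time is a proxy for dose.

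The rest does not carry. The understatement depends on which figure slipped, and the same sentence gives a consistent and larger maximum. An underived ceiling that overstates the likely exposure does not mislead a reader into accepting more risk than is disclosed, and the section also reports the doses previously observed. To say that the ceiling leaves no usable protection overlooks the two-minute cap and the other controls in Data Collection.

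Recording a dose reading from the fluoroscopy unit assumes that the unit displays one, and that the reading can be turned into effective dose, the quantity that is limited. Neither is established. Parts of the document were also unavailable for review, so a dose-recording provision elsewhere cannot be excluded.

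**Conclusion.** No change to the plan follows. The mismatch in the previous study's mean is real and its size is exactly a factor of 10. It is a clerical slip in background text, to be reconciled against the source data when the text is next edited. It leaves the Negligible label, the 2-rem ceiling, the two-minute cap and the analysis as they are.

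The factor of 12 between the ceiling and the two-minute dose at the typical rate is a declared margin, not an arithmetic error. What is missing is the derivation, which is a gap in explanation. Noting a dose reading beside on-time would be an optional addition, with no demonstrated gain in protection under the existing cap.

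This rests on two assumptions: that 10 mSv per rem is the intended conversion, as three of the four pairs show, and that the dose rate in this study is not of an order 12 times the highest rate quoted. The second cannot be verified from the document. The previous study's maximum of 0.27 mSv under the same two-minute limit makes it reasonable.

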## 2. Participant Confidentiality

The investigator will ensure patient confidentiality to the extent that is permissible by law is maintained throughout the study and after. Complete confidentiality cannot be guaranteed.

### Hard Copy

In compliance with HIPAA regulations, all participants will have their identities withheld from all public files. The personnel in the following list will have access to participant PHI for the purposes of recruitment or compliance and/or may have contact with patients:

### Clinical Observations:

There are no clinical observations made during this data collection or from the images obtained through data collection. There will be no radiology report generated for this procedure conducted as a result of this study. Therefore, no RT will review such a report for the procedures, which would be the only way such a "significant problem" would be determined. It is not anticipated that the imaging collected during this study would potentially provide benefit to specific subjects by influencing Cr. [name]' treatment plan.

### BENEFITS

The potential benefits from this study include, but are not limited to:

- Better understanding of the joints analyzed with the same technique in the past.
- Future implant design improvements based on the kinematic findings.
- New and advanced surgical techniques for TKA based on the results.

- There is no intention of any direct benefit to participants of the study accept they will be able to see their implant on the video monitor and the fluoroscopic video will be assessed by the research team.
